8.2.2 Special Assays or Procedures

Antibody and antigen assays for Histoplasmosis, blastomycosis and coccidioidomycoses will be performed at study sites using instructions for specimen handling and processing found in the Manual of Procedures.

Pharmacokinetic assessments to quantify plasma concentrations of itraconazole and hydroxyitraconazole will be performed by a Central Laboratory. Instructions for specimen handling, storage, and shipping are found in the Manual of Procedures.

8.3 Quality of Life (QOL) Evaluations

8.3.1 Short Form 12 Version 2 (SF-12v2)

The SF-12v2 is a 12-question multipurpose survey instrument derived from the larger, SF-36 [17]. The SF-12v2 has been used in numerous healthcare settings and disease types to help determine the patient's overall state of wellbeing and health-related QOL by means of assessing both physical and mental status at the time of the survey. The 8 domains of the survey are: physical functioning (PF), role-physical (RP), bodily pain (BP), general health (GH), vitality (VT), social functioning (SF), role-emotional (RE), and mental health (MH). Subjects will be administered the SF-12PK at Day 1, Day 42, and Day 180. Version 2 of the SF-12 (Optum) will be used for this study.

8.4 Methods and Timing for Assessing, Recording, and Analyzing Safety Parameters

8.4.1 Adverse Events

ICH E6 defines an AE as any untoward medical occurrence in a patient or clinical investigation subject administered a pharmaceutical product regardless of its causal relationship to the study treatment. An AE can therefore be any unfavorable and unintended sign (including an abnormal laboratory finding), symptom, or disease temporally associated with the use of medicinal (investigational) product. The occurrence of an AE may come to the attention of study personnel during study visits and interviews of a study recipient presenting for medical care, or upon review by a study monitor.

All AEs including local and systemic reactions not meeting the criteria for "serious adverse events" should be captured on the appropriate CRF. Information to be collected includes event description, time of onset, clinician's assessment of severity, relationship to study product (assessed only by those with the training and authority to make a diagnosis, which would include MD, PA, Nurse Practitioner, DO, or DDS), and time of resolution/stabilization of the event. All AEs occurring while on study must be documented appropriately regardless of relationship. All AEs will be followed to adequate resolution.

Any medical condition that is present at the time that the patient is screened should be considered as baseline and not reported as an AE. However, if it deteriorates at any time during the study, it should be recorded as an AE.

All AEs must be graded for severity and relationship to study product.

FDA defines an AE as any untoward medical occurrence associated with the use of a drug in humans, whether or not considered drug related.

Severity of Event: All AEs will be assessed by the clinician using a protocol defined grading system. For events not included in the protocol defined grading system, than the following guidelines will be used to quantify intensity.

- Mild: events require minimal or no treatment and do not interfere with the patient's daily activities.
- Moderate: events result in a low level of inconvenience or concern with the therapeutic measures. Moderate events may cause some interference with functioning.
- Severe: events interrupt a patient's usual daily activity and may require systemic drug therapy or other treatment. Severe events are usually incapacitating.
- Life threatening: any adverse drug experience that places the patient or subject, in the view of the investigator, at immediate risk of death from the reaction as it occurred, i.e., it does not include a reaction that had it occurred in a more severe form, might have caused death.

Changes in the severity of an AE should be documented to allow an assessment of the duration of the event at each level of intensity to be performed. Adverse events characterized as intermittent require documentation of onset and duration of each episode.

Relationship to Study Products: The clinician's assessment of an AE's relationship to test article (study drug) is part of the documentation process, but it is not a factor in determining what is or is not reported in the study. If there is any doubt as to whether a clinical observation is an AE, the event should be reported. All AEs must have their relationship to study product assessed using the terms: related or not related. In a clinical trial, the study product must always be suspect. To help assess, the following guidelines are used.

- Related There is a reasonable possibility that the study product caused the
 adverse event. Reasonable possibility means that there is evidence to suggest a
 causal relationship between the study product and the adverse event.
- Not Related There is not a reasonable possibility that the administration of the study product caused the event.

8.4.2 Serious Adverse Events

An adverse event or suspected adverse reaction is considered "serious" if, in the view of either the investigator or sponsor, it results in any of the following outcomes:

- Death,
- a life-threatening adverse event*,
- inpatient hospitalization or prolongation of existing hospitalization,
- a persistent or significant incapacity or substantial disruption of the ability to conduct normal life functions, or
- a congenital anomaly/birth defect.
- Important medical events that may not result in death, be life-threatening, or require hospitalizations may be considered serious when, based upon appropriate medical judgment they may jeopardize the patient or subject and may require medical or surgical intervention to prevent one of the outcomes listed in this definition. Examples of such medical events include allergic bronchospasm requiring intensive treatment in an emergency room or at home, blood dyscrasias or convulsions that do not result in inpatient hospitalization, or the development of drug dependency or drug abuse.
- * Life-threatening adverse event: an adverse event is considered "life-threatening" if, in the view of either the investigator or sponsor, its occurrence places the patient or subject at immediate risk of death. It does not include an adverse event, had it occurred in a more severe form, might have caused death.

All SAEs will be:

- recorded on the appropriate SAE CRF
- followed through resolution by a study clinician
- reviewed and evaluated by a study clinician

8.5 Reporting Procedures

8.5.1 Serious Adverse Events

AEs will be followed until resolution even if this extends beyond the study-reporting period. Resolution of an AE is defined as the return to pretreatment status or stabilization of the condition with the expectation that it will remain chronic.

Any AE that meets a protocol-defined serious criterion must be submitted immediately (within 24 hours of site awareness) on an SAE form (located in the Manual of Procedures) to the MSG Coordinating Center at the University of Alabama in Birmingham.

Contact:

[name]

Mycoses Study Group Administrator
University of Alabama at Birmingham, Infectious Diseases Division
[name]
[name]
[contact]
[contact]
Email [contact]

Other supporting documentation of the event should be provided immediately or as soon as possible.

The Study Principal Investigator will be notified of the SAE by the MSG Coordinating Center and will review and assess the SAE for regulatory reporting and potential impact on study subject safety and protocol conduct.

At any time after completion of the study, if the investigator becomes aware of an SAE that is suspected as being related to study product, the investigator will report the event to the MSG Coordinating Center who will notify Mayne Pharma.

8.5.2 Regulatory Reporting

The MSG Coordinating Center, will report any suspected adverse reaction that is both serious and unexpected. The MSG Coordinating Center will report an adverse event as a suspected adverse reaction only if there is evidence to suggest a causal relationship between the drug and the adverse event. The MSG Coordinating Center will notify FDA, Mayne Pharma, and all participating investigators (i.e., all investigators to whom the sponsor is providing drug under the IND) in an IND safety report of potential serious risks from clinical trials or any other source, as soon as possible, but in no case later than 15 calendar days after the sponsor determines that the information qualifies for reporting as specified in 21 CFR Part 312.32. The MSG Coordinating Center will also notify FDA of any unexpected fatal or life-threatening suspected adverse reaction as soon as possible but in no case later than 7 calendar days after the sponsor's initial receipt of the information. Relevant follow up information to an IND safety report will be submitted as soon as the information is available. Upon request from FDA, the MSG Coordinating Center will submit to FDA any additional data or information that the

agency deems necessary, as soon as possible, but in no case later than 15 calendar days after receiving the request.

All serious events designated as "not related" to study product(s), will be reported to the FDA at least annually in a summary format.

8.6 Safety Oversight (Data Review Committee)

Safety oversight will be under the direction of the study designated Data Review Committee (DRC). The DRC will meet to assess safety and efficacy data on each arm of the study. The DRC will review aggregate safety data for increased rate of occurrence of serious suspected adverse reactions. The DRC will operate under the rules of a charter that will be written at the organizational meeting of the DRC. At this time, each data element that the DRC needs to assess will be clearly defined. The DRC will advise the study team of its findings.

9 CLINICAL MONITORING

9.1 Site Monitoring Plan

Trial monitoring is an integral component of trial quality assurance and critical for ICH GCP fulfillment. According to the International Council for Harmonisation E6 Good Clinical Practice (R2), and the FDA Title 21 CFR, Part 312, Subpart D, Responsibilities of the Sponsor. The sponsor should determine the appropriate extent and nature of monitoring based on the study objectives, purpose, design, complexity, blinding, size and endpoints. ICH states that naturally, there is a need for on-site monitoring, but there are circumstances when remote or central monitoring may be permitted. These regulations incorporated risk-based monitoring in the most recent revision encouraging the sponsor to rationalize the blend of monitoring (on-site, combination of on-site and centralized monitoring, or only remote monitoring).

Risk-based monitoring is defined by the FDA Guidance for Industry Oversight of Clinical Investigations — A Risk-Based Approach to Monitoring, as focused sponsor oversight activities on preventing or mitigating important and likely risks to data quality and processes critical to human subject protection and trial integrity. The approach the sponsor has approved for this study is a hybrid of on-site and centralized monitoring. Qualification visit will be performed on-site with all the assigned study staff present and facilities inspected. Site Initiation and Training can be performed remotely or on-site, based on the availability of the site staff.

Routine monitoring activities will be performed both on-site periodically, as is possible and safe related to the ongoing COVID-19 precautions, with the primary process being remote monitoring of the regulatory files and electronic case report forms to identify potential issues.

A site monitor will be appointed as an unbiased and independent party to perform various study visits to evaluate the site's capabilities and monitor the ongoing progress of a clinical study. Over the course of the study, the role of the site monitor is to verify the following on behalf of the study team at the appointed site:

- The rights, well-being, and safety of human subjects are protected.
- Reported trial data are accurate, complete, and verifiable from source documents.
- The conduct of the trial is in compliance with the currently approved Protocol, GCP, and applicable regulatory requirements.

10 STATISTICAL CONSIDERATIONS

10.1 Study Hypotheses and Statistical Analyses

For the primary outcomes of Stage I, t- and chi-square tests will be used to test whether the treatment group experiences superior PK at Day 14 and Tolerability at Day 42, respectively. If it is determined that the assumptions of the t-test are not met by the data, non-parametric statistical tests will be employed; Fisher's exact test will be used as deemed necessary. In the unusual occurrence that the study groups are not in equipoise with respect to the measured baseline demographic, behavioral and clinical characteristics, linear and logistic regression models will be used to compare the treatment groups, adjusted for any observed differences. The same aforementioned statistics techniques will be used for the secondary outcomes of Stage I as well as the primary and secondary outcomes of Stage II.

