States, Canada and Central/South America (Approximately: 40 Histoplasmosis, 20 Coccidioidomycosis, 20 other endemic mycoses)

Number of Sites: Approximately 20 total sites in US, Canada, and Central/South

America

Study Duration: This study is estimated to be opened for 18 months after initiation (12

month patient accrual, 6 month treatment period).

Subject Each participant will be enrolled in the study for 180 days

Participation

Objectives:

The objectives of this study are to compare PK, tolerance, safety, and efficacy of SUBA-Itraconazole study drug versus conventional itraconazole in a randomized open-label trial followed by a second stage of continuing open-label study drug.

Stage I - Randomized, Open-Label, Parallel Group

Primary Objective

- PK at Day 14
- Tolerability at Day 42

Secondary Objective

- PK at Day 7
- PK at Day 42
- Efficacy by Day 42
- Safety by Day 42
- QOL (including hospital/ICU visits) Assessments by Day 42

Stage II - Open-Label Extension

Primary Objective

- Efficacy by Day 180
- Tolerability by Day 180

Secondary Objective

- Safety by 180
- QOL (including hospital/ICU visits) Assessments by Day 180

Description of Study Design:

[figure not shown]
This is a prospective, multi-center, randomized, open-label parallel arm study involving patients with proven or probable invasive endemic fungal infection to ascertain the pharmacokinetics, safety, efficacy, tolerability and health economics of oral SUBA-itraconazole compared to conventional itraconazole. Patients will receive randomized open-label study drug (SUBA-itraconazole or conventional itraconazole) over a 42 day period and then continue therapy until Day 180 or earlier if Principal Investigator determines discontinuation of therapy is safe. Patients will be stratified based on clinically reported infection with the human immunodeficiency virus (HIV).

The study sample size will be 80 evaluable patients – target enrollment (three groups: approximately 40 histoplasmosis, 20 coccidioidomycosis, 20 other endemic fungal infections).

Estimated Time to Complete Enrollment

12 Months

Schematic of Study Design:

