5.3 Treatment Assignment Procedures

5.3.1 Randomization Procedures

Stratified randomization will be used to assign qualifying participants to either conventional itraconazole or SUBA-itraconazole and dosed according to HIV status (positive or negative by clinical self-report) (Section 6.2).

Randomization procedures are described in the Manual of Procedures.

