10.2 Sample Size Considerations

The study will randomize 80 adults infected with one of the endemic mycoses living in the United States, Canada and Central/South America (40 Histo, 20 Cocci, 20 other endemic mycoses). This sample size provides adequate power (77%) to reject the null hypothesis of equal pharmacokinetic means when the population mean difference is $\mu 1$ - $\mu 2$ = 231.7 - 291.7 = -60.0 with standard deviations of 94.0 and 101.8 for the study groups, and with a significance level (alpha) of 0.050 using a two-sided two-sample unequal-variance t-test.

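### Section 10.1 lets observed imbalance decide covariate adjustment, with no threshold, covariate list or primary-result rule, and plans no term for the HIV randomization stratum

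*Combined protocol and SAP*

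**What the plan says.** Section 10.1 sets the default for the Stage I primary outcomes: "t- and chi-square tests will be used to test whether the treatment group experiences superior PK at Day 14", with the chi-square test for tolerability at Day 42. A non-parametric test or Fisher's exact test is the fallback.

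It then adds a conditional route. The condition is worded this way: "In the unusual occurrence that the study groups are not in equipoise with respect to the measured baseline demographic, behavioral and clinical characteristics". When that condition is judged to be met, the plan says that "linear and logistic regression models will be used to compare the treatment groups, adjusted for any observed differences". Three broad classes of characteristic are named, but no variable, test, p-value or standardized difference. Nothing says whether the adjusted result replaces the unadjusted one or supplements it.

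The scope is wide: "The same aforementioned statistics techniques will be used for the secondary outcomes of Stage I", and for all Stage II outcomes as well.

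On design, section 5.3.1 says "Stratified randomization will be used to assign qualifying participants" and gives self-reported HIV status as the factor; the Protocol Summary also names HIV. For detail, "Randomization procedures are described in the Manual of Procedures". HIV is not mentioned in section 10. Section 10.2 computes power "using a two-sided two-sample unequal-variance t-test", with no covariate or stratum.

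**The concern.** The model for the headline comparison is not fixed before the data are seen. Whether it is adjusted, and for what, depends on a judgement about imbalance that the plan leaves open, in a trial that is open-label throughout. The plan presents imbalance as exceptional, but with 80 patients and several baseline variables some imbalance by chance is ordinary. Two analysts following section 10.1 in good faith could report different primary p-values.

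The HIV stratum adds a smaller point. Stratifying is meant to balance HIV between the arms. A rule that admits only imbalanced variables therefore tends to leave out the one variable the design singled out.

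**Working it through.** **Inputs.** From section 10.2: 80 patients, difference 60.0, SDs 94.0 and 101.8, two-sided alpha 0.05, power 77%. Assumed, because the documents do not give them: 1:1 allocation (40 per arm), number of baseline variables, HIV share, and the strength of HIV as a predictor.

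**1. The plan's own figure.** SE = sqrt(94.0²/40 + 101.8²/40) = sqrt(220.9 + 259.1) = 21.91. Noncentrality = 60/21.91 = 2.74, with Welch df 77.5. Power is 77.2%, so the stated 77% reproduces. It is the power of the unadjusted test.

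**2. How often the trigger fires by chance.** For k independent variables, each tested at 0.05, P(at least one flagged) = 1 − 0.95^k:

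| k | p<0.05 trigger |
|---|---|
| 5 | 22.6% |
| 10 | 40.1% |
| 20 | 64.2% |

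A standardized-difference trigger of 0.2 is much laxer. Its SE at 40 per arm is sqrt(2/40) = 0.2236, so one variable is flagged with probability 0.371. At least one is flagged in 1 − 0.629^5 = 90% (k = 5) or 1 − 0.629^10 = 99% (k = 10) of trials.

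**3. What the missing rule can do.** These are simulation results with 40 per arm and 5 or 10 independent covariates that jointly explain 0, 10 or 30% of outcome variance. The five readings are: unadjusted; adjusted for covariates with baseline p<0.05, p<0.10 or p<0.20; and adjusted for those with standardized difference >0.2.

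| Use of the rule | Type I error | Readings disagree on significance, planned effect present |
|---|---|---|
| Any one reading, fixed in advance | 3.3-5.3% | not applicable |
| Better of unadjusted and p<0.05 trigger | about 5-6% | about 2-5% of trials |
| Best of all five | 6.0-7.5% | 6-19% of trials |

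**4. HIV and the PK mean comparison.** Suppose HIV is balanced between arms and explains a share R² of outcome variance. The true SE is then 21.91·sqrt(1 − R²), while the unadjusted test goes on using about 21.91. At R² = 10% the true SE is 20.79. The unadjusted test rejects when the difference exceeds 1.99 × 21.91 = 43.6, which is 43.6/20.79 = 2.10 true standard errors. Its actual type I error is therefore about 3.6%, which is conservative.

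| R² | Unadjusted power | Adjusted power | Gain (points) |
|---|---|---|---|
| 0 | 77.3% | 77.2% | about 0 |
| 5% | 77.9% | 79.2% | 1.3 |
| 10% | 78.5% | 81.4% | 2.9 |

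The HIV difference implied by R² is sqrt(R²)·98.0/sqrt(p(1 − p)), where p is the HIV-positive share. At R² = 10% this is 62.0 for p = 0.5 and 77.5 for p = 0.2. Both exceed the planned drug difference of 60, so a larger R² is hard to argue for.

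**5. Would the trigger admit HIV?** With blocks of 4 within stratum (assumed), HIV was flagged at p<0.05 in 0 of 5,000 simulated trials at 10, 20 or 50% HIV-positive. With simple randomization it was flagged in 5.1-5.7%.

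**6. Tolerability.** Take 20% HIV-positive and 90% retention in HIV-negative patients. As retention in HIV-positive patients goes from 50% to 90%, the chi-square type I error runs from 3.2% to 5.9%. An HIV-stratified Cochran-Mantel-Haenszel (CMH) test stays at 4.8-5.0%. The chi-square test is clearly conservative only when the HIV gap is very large.

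**The case against.** The best defence is that adjustment is reserved for exceptional cases. On that view the lax triggers (p<0.20, standardized difference >0.2) are not fair readings, and it is these that push the best-of-five figure to 6-7.5%. This stands: that range is a worst case, and the conventional comparison gives about 5-6%. But even a p<0.05 trigger fires in 23-40% of trials with 5 to 10 variables, so no ordinary threshold makes the route exceptional.

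Second, HIV could enter the regression as a clinical characteristic, so it is not excluded outright. That is right. How rarely it would enter depends on blocking details held in the Manual of Procedures, which is not in the file. Section 6.5.2 lists one antiretroviral that lowers itraconazole levels and two that raise them, so the net effect of HIV may be near zero. Taken alone, the HIV part is a matter of efficiency.

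Third, declaring the existing unadjusted tests primary would also end the free choice and keep the 77%. It would. Including the stratum is preferable because the analysis then matches the randomization, and it costs almost nothing.

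A reader might infer that section 10.1 as written inflates type I error, or that leaving out HIV invalidates the PK test. The documents support neither. Any reading fixed in advance stays near or below 5%, and inflation needs a choice made after the results are seen, which the plan permits but does not describe. Omitting a prognostic stratum makes the PK mean comparison conservative.

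**Conclusion.** The point holds as a pre-specification gap of modest size. The plan does not say when adjustment happens, for which variables, or which result counts. The cost in error rate runs from nothing, if one reading is fixed beforehand, through about 5-6% with conventional readings, to about 6-7.5% at worst. The stratum part is secondary: 0-3 power points for the PK mean comparison at R² of 0-10%.

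These sizes rest on 1:1 allocation, independent baseline variables of assumed number, and assumed HIV share and effect. The statement that an imbalance trigger would rarely admit HIV further assumes randomization balanced within HIV strata. The change is worth making because it is cheap and settles the primary result in advance.

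**What to change.** In section 10.1:

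1. Delete imbalance-triggered adjustment as a route to the primary result.
2. Pre-specify the comparison of PK means as a linear model with arm and the HIV stratum as randomized, allowing unequal variances by arm (for example HC2 standard errors). Use a van Elteren test if a non-parametric analysis is needed.
3. Pre-specify the tolerability comparison as an HIV-stratified CMH test.
4. Report the unadjusted t- and chi-square tests as supportive.
5. Name any further covariates in advance and keep them few.

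In section 10.2, note that the 77% is for the unadjusted Welch test and is about the same or slightly higher with HIV adjustment.

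Two limits apply. The linear model does not cover the coefficient-of-variation component in section 10.3. A stratified log-rank test would not suit time to a level above 500 mcg/L: Appendix A schedules PK samples only at Days 7, 14 and 42, so attainment is seen only at visits.

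The cost is wording and one degree of freedom. If HIV is not prognostic, simulated power is unchanged: 76.9% with HC2 against 77.0% unadjusted for PK, and 79.2% with CMH against 79.1% with chi-square for tolerability at an assumed 90% versus 65%. An exact CMH test would lower the last figure to 71.6%, the same as the plan's Fisher fallback, so keep it for sparse data. A long covariate list also costs power: 74.5% with 5 non-prognostic covariates and 71.2% with 10.
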